# 6.11.1. Management of Virologic Rebound

Subjects who meet the criteria listed below will be considered to have virologic rebound:

- At any post Day 1 visit, a rebound in HIV-1 RNA ≥ 50 copies/mL, which is subsequently confirmed at the following scheduled or unscheduled visit; OR
- Any subject with HIV RNA  $\geq$  50 copies/mL at study drug discontinuation

Following the unconfirmed virologic rebound, subjects will be asked to return to the clinic for a scheduled or unscheduled blood draw (2 to 3 weeks after the date of the original test that resulted in HIV-1 RNA virologic rebound) for confirmation of virologic rebound. If virologic rebound is confirmed at the scheduled or unscheduled visit and the HIV-1 RNA is  $\geq$  200 copies/mL, the blood sample from the confirmation visit will be the primary sample used for HIV-1 genotypic

and phenotypic testing. After a subject's first post-baseline resistance test, additional testing will be conducted on a case-by-case basis. Any subject may be discontinued at Investigator's discretion or per local treatment guidelines.

[figure not shown]
If no resistance is detected from the genotype or phenotype, the subject may remain on study drugs and HIV-1 RNA test should be repeated (2 to 3 weeks after date of test with HIV-1 RNA ≥ 50 copies/mL). Investigators should carefully evaluate the benefits and risks of remaining on study drug for each individual subject and document this assessment in the on-site medical record.

Subjects who are noncompliant on an ongoing basis will be considered for discontinuation per the Investigator's discretion or local treatment guidelines. Investigators who opt to discontinue study drugs for an individual subject must discuss with the Medical Monitor prior to study drug discontinuation.

For subjects who are off study drug but remain on study, it will be the Investigator's discretion to manage virologic rebound.

Please refer to Figure 6-1 for the management of subjects who meet the criteria for virologic rebound.

Figure 6-1. Virologic Rebound Schema

- If virologic rebound is not confirmed, the subject will remain on their current regimen.
- b. If virologic rebound is confirmed and the HIV-1 RNA is ≥ 200 copies/mL, the HIV-1 genotype and phenotype (reverse transcriptase, protease, and integrase) will be analyzed.
- c. Based on the results of the genotypic and phenotypic assays, the subject will remain on study drugs or study drugs will be discontinued. If genotyping or phenotyping fails, a new ARV regimen may be configured at the discretion of the Investigator.
- d. If no new resistance is detected, HIV-1 RNA will be repeated (2-3 weeks later). Investigator reviews study drug continuation/discontinuation options and discusses with the Medical Monitor prior to study drug discontinuation
- e. A new ARV regimen will be configured, at the Investigator's discretion, and the subject will remain in the study.

# 6.11.2. Subjects with HIV-1 RNA ≥ 50 copies/mL at Study Drug Discontinuation, or Week 48

Subjects with HIV-1 RNA  $\geq$  50 copies/mL at study drug discontinuation, or last visit, or Week 48 will be considered virologic failures. Subjects with HIV-1 RNA  $\geq$  50 copies/mL at Week 48, will be asked to return for an unscheduled visit within the visit window for a retest.

Subjects with HIV-1 RNA  $\geq$  200 copies/mL at study drug discontinuation, last visit, or Week 48, will also have resistance testing conducted.

#### 7. ADVERSE EVENTS AND TOXICITY MANAGEMENT

# 7.1. Definitions of Adverse Events, Adverse Reactions, and Serious Adverse Events

#### 7.1.1. Adverse Events

An adverse event is any untoward medical occurrence in a clinical study subject administered a medicinal product, which does not necessarily have a causal relationship with the treatment. An AE can therefore be any unfavorable and/or unintended sign, symptom, or disease temporally associated with the use of a medicinal product, whether or not considered related to the medicinal product. AEs may also include pre- or post-treatment complications that occur as a result of protocol specified procedures, lack of efficacy, overdose, drug abuse/misuse reports, or occupational exposure. Preexisting events that increase in severity or change in nature during or as a consequence of participation in the clinical study will also be considered AEs.

An AE does not include the following:

- Medical or surgical procedures such as surgery, endoscopy, tooth extraction, and transfusion. The condition that led to the procedure may be an adverse event and must be reported.
- Pre-existing diseases, conditions, or laboratory abnormalities present or detected before the screening visit that do not worsen
- Situations where an untoward medical occurrence has not occurred (eg, hospitalization for elective surgery, social and/or convenience admissions)
- Overdose without clinical sequelae (see Section 7.6.1)
- Any medical condition or clinically significant laboratory abnormality with an onset date before the consent form is signed and not related to a protocol-associated procedure is not an AE. It is considered to be pre-existing and should be documented on the medical history eCRF.

#### 7.1.2. Serious Adverse Events

A **serious adverse event** is defined as an event that, at any dose, results in the following:

- Death
- Life-threatening (Note: The term "life-threatening" in the definition of "serious" refers to an event in which the subject was at risk of death at the time of the event; it does not refer to an event that hypothetically might have caused death if it were more severe.)
- In-patient hospitalization or prolongation of existing hospitalization

- Persistent or significant disability/incapacity
- A congenital anomaly/birth defect
- A medically important event or reaction: such events may not be immediately life-threatening or result in death or hospitalization but may jeopardize the subject or may require intervention to prevent one of the other outcomes constituting SAEs. Medical and scientific judgment must be exercised to determine whether such an event is a reportable under expedited reporting rules. Examples of medically important events include intensive treatment in an emergency room or at home for allergic bronchospasm; blood dyscrasias or convulsions that do not result in hospitalization; and development of drug dependency or drug abuse. For the avoidance of doubt, infections resulting from contaminated medicinal product will be considered a medically important event and subject to expedited reporting requirements.

# 7.1.3. Clinical Laboratory Abnormalities and Other Abnormal Assessments as Adverse Events or Serious Adverse Events

Laboratory abnormalities without clinical significance are not recorded as AEs or SAEs. However, laboratory abnormalities (eg, clinical chemistry, hematology, and urinalysis) that require medical or surgical intervention or lead to IMP interruption, modification, or discontinuation must be recorded as an AE, as well as an SAE, if applicable. In addition, laboratory or other abnormal assessments (eg, electrocardiogram, x-rays, vital signs) that are associated with signs and/or symptoms must be recorded as an AE or SAE if they meet the definition of an AE or SAE as described in Sections 7.1.1 and 7.1.2. If the laboratory abnormality is part of a syndrome, record the syndrome or diagnosis (eg, anemia), not the laboratory result (ie, decreased hemoglobin).

For specific information on handling of clinical laboratory abnormalities in this study, please refer to Section 7.5.

#### 7.2. Assessment of Adverse Events and Serious Adverse Events

The investigator or qualified subinvestigator is responsible for assessing AEs and SAEs for causality and severity, and for final review and confirmation of accuracy of event information and assessments.

# 7.2.1. Assessment of Causality for Study Drugs and Procedures

The investigator or qualified subinvestigator is responsible for assessing the relationship to IMP therapy using clinical judgment and the following considerations:

- No: Evidence exists that the adverse event has an etiology other than the IMP. For SAEs, an alternative causality must be provided (eg, pre-existing condition, underlying disease, intercurrent illness, or concomitant medication).
- Yes: There is reasonable possibility that the event may have been caused by the investigational medicinal product.

It should be emphasized that ineffective treatment should not be considered as causally related in the context of adverse event reporting.

The relationship to study procedures (eg, invasive procedures such as venipuncture or biopsy) should be assessed using the following considerations:

- No: Evidence exists that the adverse event has an etiology other than the study procedure.
- Yes: The adverse event occurred as a result of protocol procedures, (eg, venipuncture)

# 7.2.2. Assessment of Severity

AE severity should be recorded and graded according to the Gilead Grading Scale for Severity of Adverse Events and Laboratory Abnormalities (Appendix 4). For adverse events associated with laboratory abnormalities, the event should be graded on the basis of the clinical severity in the context of the underlying conditions; this may or may not be in agreement with the grading of the laboratory abnormality.

The distinction between the seriousness and the severity of an adverse event should be noted. Severe is a measure of intensity; thus, a severe reaction is not necessarily a serious reaction. For example, a headache may be severe in intensity, but would not be classified as serious unless it met one of the criteria for serious events.

For AEs associated with laboratory abnormalities, the event should be graded on the basis of the clinical severity in the context of the underlying conditions; this may or may not be in agreement with the grading of the laboratory abnormality.

# 7.3. Investigator Requirements and Instructions for Reporting Adverse Events and Serious Adverse Events to Gilead

Requirements for collection prior to study drug initiation:

After informed consent, but prior to initiation of study medication, the following types of events should be reported on the eCRF:

• all SAEs and adverse events related to protocol-mandated procedures.

#### 7.3.1. Adverse Events

Following initiation of study medication, collect all AEs, regardless of cause or relationship, until 30-days after last administration of study IMP must be reported to the eCRF database as instructed.

All AEs should be followed up until resolution or until the adverse event is stable, if possible. Gilead may request that certain AEs be followed beyond the protocol defined follow up period.

## 7.3.2. Serious Adverse Events

All SAEs, regardless of cause or relationship, that occurs after the subject first consents to participate in the study (ie, signing the informed consent) and throughout the duration of the study, including the protocol-required post treatment follow-up period, must be reported to the eCRF database and Gilead PVE as instructed. This also includes any SAEs resulting from protocol-associated procedures performed after informed consent is signed.

Any SAEs and deaths that occur after the post treatment follow-up visit but within 30-days of the last dose of study IMP, regardless of causality, should also be reported.

Investigators are not obligated to actively seek SAEs after the protocol defined follow up period; however, if the investigator learns of any SAEs that occur after study participation has concluded and the event is deemed relevant to the use of IMP, he/she should promptly document and report the event to Gilead PVE.

# Electronic Serious Adverse Event Reporting Process

- Site personnel record all SAE data in the eCRF database and from there transmit the SAE information to Gilead PVE within 24 hours of the investigator's knowledge of the event. Detailed instructions can be found in the eCRF completion guidelines.
- If it is not possible to record and submit the SAE information electronically, because the eCRF database cannot be accessed or is not available (including at study start), record the SAE on the paper serious adverse event report form and submit by e-mail or fax within 24 hours of the investigator's knowledge of the event to:

Gilead PVE contact information: Email: PPD Fax: PPD

- As soon as it is possible to do so, any SAE reported via paper must be transcribed into the eCRF Database according to instructions in the eCRF completion guidelines.
- If an SAE has been reported via a paper form because the eCRF database has been locked, no further action is necessary.
- All AEs and SAEs will be recorded in the eCRF database within the timelines outlined in the eCRF completion guideline.
- Additional information may be requested to ensure the timely completion of accurate safety reports.
- Any medications necessary for treatment of the SAE must be recorded onto the concomitant medication section of the subject's eCRF and the event description section of the SAE form

• For fatal or life-threatening events, copies of hospital case reports, autopsy reports, and other documents are also to be submitted by e-mail or fax only when requested and applicable. Transmission of such documents should occur without personal subject identification, maintaining the traceability of a document to the subject identifiers.

# 7.4. Gilead Reporting Requirements

Depending on relevant local legislation or regulations, including the applicable US FDA Code of Federal Regulations, the EU Clinical Trials Directive (2001/20/EC) and relevant updates, and other country-specific legislation or regulations, Gilead may be required to expedite to worldwide regulatory agencies reports of SAEs, serious adverse drug reactions (SADRs), or SUSARs. In accordance with the EU Clinical Trials Directive (2001/20/EC), Gilead or a specified designee will notify worldwide regulatory agencies and the relevant IEC in concerned Member States of applicable SUSARs as outlined in current regulations.

Assessment of expectedness for SAEs will be determined by Gilead using reference safety information specified in the investigator's brochure, EU Summary of Product Characteristics (SmPC), or relevant local label as applicable.

All investigators will receive a safety letter notifying them of relevant SUSAR reports associated with any study IMP. The investigator should notify the IRB or IEC of SUSAR reports as soon as is practical, where this is required by local regulatory agencies, and in accordance with the local institutional policy.

# 7.5. Toxicity Management

All clinical and clinically significant laboratory toxicities will be managed according to uniform guidelines detailed in Appendix 4 as outlined below.

- Clinical events and clinically significant laboratory abnormalities will be graded according to the Gilead Grading Scale for Severity of Adverse Events and Laboratory Abnormalities (Appendix 5).
- Grade 3 and 4 clinically significant laboratory abnormalities should be confirmed by repeat testing within 3 calendar days of receipt of results and before study drug discontinuation, unless such a delay is not consistent with good medical practice

Any questions regarding toxicity management should be directed to the Gilead Medical Monitor.

# 7.5.1. Grades 1 and 2 Laboratory Abnormality or Clinical Event

Continue study drug at the discretion of the Investigator.

## 7.5.2. Grade 3 Laboratory Abnormality or Clinical Event

• For Grade 3 clinically significant laboratory abnormality or clinical event, study drug may be continued if the event is considered to be unrelated to study drug.

- For a Grade 3 clinical event, or clinically significant laboratory abnormality confirmed by repeat testing, that is considered to be related to study drug, study drug will be withheld until the toxicity returns to ≤ Grade 2. When restarting study drug following resolution of the adverse event, the study drug should be restarted at full dose upon discussion with the Gilead Medical Monitor.
- If a laboratory abnormality recurs to ≥ Grade 3 following rechallenge with study drug and is considered related to study drug, then study drug will be permanently discontinued and the subject managed according to local practice. Recurrence of laboratory abnormalities considered unrelated to study drug may not require permanent discontinuation but requires discussion with the Gilead Medical Monitor.

# 7.5.3. Grade 4 Laboratory Abnormality or Clinical Event

- For a Grade 4 clinical event or clinically significant Grade 4 laboratory abnormality confirmed by repeat testing that is considered related to study drug, study drug will be permanently discontinued and the subject managed according to local practice. The subject should be followed as clinically indicated until the laboratory abnormality returns to baseline or is otherwise explained, whichever occurs first. A clinically significant Grade 4 laboratory abnormality that is not confirmed by repeat testing should be managed according to the algorithm for the new toxicity grade.
- Study drug may be continued without dose interruption for a clinically non-significant Grade 4 laboratory abnormality (eg, Grade 4 CK after strenuous exercise, or triglyceride elevation that is nonfasting or that can be medically managed) or a clinical event considered unrelated to study drug requires discussion with the Gilead Medical Monitor.

#### 7.5.4. On-Treatment ALT Flare

An On-Treatment ALT Flare is defined as:

• Confirmed (within 3 days of receipt of initial laboratory results) serum ALT >  $2 \times Day 1$  value and >  $10 \times ULN$ , with or without associated symptoms.

## 7.5.4.1. Management of ALT Flare in Subjects Receiving Study Medication

If laboratory results indicate elevation of ALT  $> 2 \times Day 1$  value and  $> 10 \times ULN$ , the following is recommended:

- Schedule the subject to return to the clinic as soon as possible (ideally within 3 days after initial laboratory results were drawn). During the visit, a clinical assessment of the subject will be performed. The assessment should include a physical examination and evaluation of the subject's mental status.
- If the ALT elevation is confirmed, request the central clinical laboratory to conduct reflex testing for plasma HBV DNA, HBV serology (HBsAg and HBsAb), HDV, HAV IgM, and HCV serology

Check the following laboratory parameters: serum ALT and AST, total bilirubin, and serum albumin. Based on the results of the confirmatory tests, the following treatment modifications are recommended:

# Elevated Liver Enzymes, Normal or Stable relative to Day 1 Liver Function Tests

If ALT levels are elevated (ie,  $> 2 \times Day 1$  and  $> 10 \times ULN$ ) with normal or stable total bilirubin, the subject may remain on study medication and should be monitored weekly as long as ALT levels return to normal or Day 1 level. During monitoring, if the ALT values remain persistently elevated, the Investigator should discuss with the Gilead Medical Monitor whether the study drug should be discontinued.

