# **Elevated Liver Enzymes, Elevated Liver Function Tests**

If ALT values are elevated (ie,  $> 2 \times Day 1$  and  $> 10 \times ULN$ ), and total bilirubin is confirmed to be 2 x Day 1 value, provided both are > ULN, the investigator should consider discontinuing study medication (upon discussion with the Gilead Medical Monitor, unless the safety of the patient is of immediate concern). The subject should be monitored weekly as long as ALT, and total bilirubin remain elevated or above Day 1 values.

During monitoring, if the ALT values and the liver function tests remain persistently elevated, the Investigator should discuss with the Gilead Medical Monitor whether the study drug should be discontinued.

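### A confirmed, clinically significant, drug-related ALT above 10 × ULN meets a mandatory stop in Protocol 7.5.3 and a permissive rule in 7.5.4.1, and the text does not say which governs

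*Protocol*

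**What the plan says.** **General Grade 4 rule (Protocol 7.5.3).** For a "clinically significant Grade 4 laboratory abnormality confirmed by repeat testing that is considered related to study drug, study drug will be permanently discontinued". The same section has a let-out: "Study drug may be continued without dose interruption for a clinically non-significant Grade 4 laboratory abnormality". It also mentions clinical events thought unrelated to study drug. ALT flare is not named as an exception.

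**Grading (Protocol Appendix 4, enzymes).** Grade 4 ALT is any value above 10 × ULN.

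**ALT flare definition (Protocol 7.5.4).** A confirmed ALT that is both more than twice the Day 1 value and above 10 × ULN, "with or without associated symptoms". The definition does not ask whether the event is related to study drug.

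**ALT flare management (Protocol 7.5.4.1).** The steps are introduced as recommendations.
- Normal or stable bilirubin: "the subject may remain on study medication and should be monitored weekly as long as ALT levels return to normal or Day 1 level". The next sentence begins: "During monitoring, if the ALT values remain persistently elevated, the Investigator should discuss with the Gilead Medical Monitor", and the subject of that discussion is whether to stop.
- Bilirubin confirmed at twice Day 1 and above ULN: "the investigator should consider discontinuing study medication", after discussion with the Medical Monitor unless safety is of immediate concern. On follow-up: "The subject should be monitored weekly as long as ALT, and total bilirubin remain elevated or above Day 1 values".

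**The concern.** An investigator with a confirmed ALT above 10 × ULN, judged clinically significant and drug-related, can open the protocol at two places and find different instructions about study drug. One is an order to stop for good. The other allows continuation, or leaves stopping to judgement. A site that turns to the flare section, which is the natural place to look for a liver value, could depart from a mandatory stopping rule without noticing.

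The organ matters in this trial. Section 7.5.5 is devoted to possible hepatobiliary toxicity and calls the human risk unknown. Subjects with chronic HBV or HCV may enrol (Protocol 4.1), and SAP 7.2.4 and 8.1 plan listings of ALT elevations and flares in HBV-coinfected subjects.

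There is also a smaller effect on the data. Protocol 7.1.3 requires a laboratory abnormality that leads to discontinuation to be recorded as an adverse event, SAP 7.1.6 tabulates adverse events that caused discontinuation, and SAP 6.1.1.2 uses the discontinuation reason to sort subjects with no value in the Week 48 window.

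**Working it through.** No sample size, power or alpha figure is involved. The check is whether the two rules cover the same events, and what each then requires.

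**1. Threshold overlap.** Let U be the ULN and D the Day 1 ALT.
- Grade 4 (Appendix 4): ALT > 10U.
- Flare (7.5.4): ALT > 10U and ALT > 2D.

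Every flare is therefore a Grade 4 ALT. The converse holds when D ≤ 5U, because then 2D ≤ 2 × 5U = 10U and any ALT above 10U already exceeds 2D. Inclusion criterion 10 limits ALT to 5 × ULN at entry, so the converse holds for anyone still within that limit on Day 1. Only the first direction is needed for the conflict.

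**2. Other conditions.** Both rules require confirmation. Section 7.5.3 adds clinical significance and relatedness before stopping becomes mandatory. Section 7.5.4.1 asks about neither.

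**3. The rules side by side, for a confirmed flare.**

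| Event | 7.5.3 | 7.5.4.1 | Relation |
|---|---|---|---|
| Not clinically significant | May continue | May remain, or consider stopping | Compatible |
| Significant, not related | No mandatory stop | May remain, or consider stopping | Compatible |
| Significant, related, bilirubin normal or stable | Permanent stop | May remain | Directly opposed |
| Significant, related, bilirubin raised | Permanent stop | Consider stopping | Mandatory against discretionary |

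**4. Which action breaches what, in the last two rows.** Stopping drug breaches neither section. Continuing is open under 7.5.4.1 and breaches 7.5.3.

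**5. Search for a tie-breaker.**
- Neither section cites the other.
- The opening of 7.5 applies its guidelines uniformly to clinically significant laboratory toxicities and makes no exception for ALT.
- Section 7.5.5 sends graded abnormalities back to 7.5 as a whole.
- Appendix 3 is listed as the management appendix, but its content was not available. The opening of 7.5 points to Appendix 4 for management and Appendix 5 for grading, whereas the appendix list puts management in Appendix 3 and grading in Appendix 4. A site following the body text would not be led to Appendix 3.

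**6. Weekly-monitoring clause.** Read literally, the stable-bilirubin sentence ties weekly monitoring to ALT returning to normal or to the Day 1 level. The following sentence deals with ALT that stays high while monitoring is under way, which presupposes that monitoring goes on in that case. The parallel sentence for raised bilirubin ties weekly monitoring to values staying elevated. The two paragraphs cover different bilirubin situations, so the clearest misfit is inside the first.

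**7. Likely frequency and effect.** In the Phase 2 study (Protocol 1.2.3.3), graded ALT abnormalities occurred in 15/64 = 23.4% on BIC+F/TAF and 3/32 = 9.4% on DTG+F/TAF. There was one Grade 3 ALT, on BIC+F/TAF, and no Grade 4 transaminase elevation in either group. Those subjects were treatment-naive, so this is only a rough guide to a switch population. Under SAP 6.1.1.2, a subject who stops for an adverse event with last on-treatment HIV-1 RNA below 50 copies/mL and no value in the window is classed as having no virologic data. That does not add to the primary endpoint count. It takes one subject out of the below-50 count, which at 260 per group is 1/260 = 0.4 percentage points, against a secondary margin of 10%.

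**The case against.** **The rules can be layered.** Section 7.5.4.1 is recommendation and permission; 7.5.3 is a mandate for a subset. An investigator who stops drug satisfies both, so a strict rule can sit on top of a looser one. This stands as far as it goes: it confines the conflict to significant, related events and shows that compliance with both is possible. It does not tell a reader of 7.5.4.1 that the stricter rule exists. The opposite convention, that the specific section overrides the general one, is equally unstated.

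**The Medical Monitor is in the pathway.** Section 7.5.5 requires prompt contact for abnormalities suggesting hepatobiliary toxicity, 7.5 sends toxicity questions to the Monitor, and both bilirubin branches call for discussion if values stay high. This makes unnoticed divergence between sites less likely, but it sets no precedence.

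**The monitoring clause can be read coherently.** The words about returning to normal could attach to remaining on study medication rather than to monitoring, or could be a slip for another conjunction. Either is plausible, so the point is editorial. The sentence still needs rewording, because it has to be guessed at.

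**Appendix 3 may already settle it.** This cannot be excluded. Even so, the body text of the two sections would remain at odds.

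A reader might also infer that sites could act in opposite ways and both be compliant. The documents do not support that: a site that continues drug after such an event breaches 7.5.3.

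**Conclusion.** The inconsistency is real but narrow. It concerns confirmed ALT above 10 × ULN that is both clinically significant and judged related to study drug. With normal or stable bilirubin the two instructions are directly opposed; with raised bilirubin they differ as mandatory against discretionary. It would be wrong to read the conflict as covering every ALT flare, since non-significant or unrelated events raise none.

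The monitoring clause is a separate and lesser matter, probably a slip.

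Few subjects should be affected, and nothing here suggests that the primary result would change. The reason to act is patient safety and consistent handling of liver events. The conclusion rests on the text available: if Appendix 3 states which section governs, what remains is a missing cross-reference in the body. No view is taken on which clinical rule is right.

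**What to change.** The sponsor's medical team should:
- reconcile 7.5.3 with both bilirubin branches of 7.5.4.1, and state in both sections which one governs a confirmed, clinically significant ALT above 10 × ULN judged related to study drug, in each bilirubin case;
- reword the weekly-monitoring sentence for normal or stable bilirubin so that it agrees with the sentence after it, and check it against the raised-bilirubin paragraph;
- check that Appendix 3 says the same, and correct the appendix numbers cited at the start of 7.5.

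The choice of rule belongs to that team. The cost is clarification wording in the protocol, with no added visits, tests or analyses.
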